ANOVA	Analysis of variance
AUC	Area under the curve
BACE	β -secretase
BChE	Butyrylcholinesterase
BDNF	Brain-derived neurotrophic factor
BID	Twice a Day
BP	Blood pressure
CDR	Clinical Dementia Rating
CFR	Code of Federal Regulations
CTCAE	Common Terminology Criteria for Adverse Events
CLBP	Chronic low back pain
Cmax	Maximum plasma and CSF concentration
ChE	Cholinesterase
CJD	Creutzfeldt-Jakob Disease
C-SSRS	Columbia Suicide Severity Rating Scale
CNS	Central Nervous System
CSF	Cerebrospinal Fluid
CV	Coefficients of variation
CVD	Cerebrovascular Dementia
DNA	Deoxyribonucleic Acid
DS	Down Syndrome
DSMB	Data Safety Monitoring Board
DSM	Diagnostic and Statistical Manual of Mental Disorders
ECG	Electrocardiogram
eCRF	Electronic Case Report Form

FCR	Fractional clearance rate
FDA	Food and Drug Administration
FSR	Fractional Synthesis Rate
FWA	Federal wide Assurance
GCP	Good Clinical Practice
GI	Gastrointestinal
GRAS	Generally recognized as safe
GWAS	Genome Wide Association Studies
HEK 293	Human embryonic kidney cells
HEENT	Head/ears/eyes/nose/throat
hERG	Human ether-a-go-go related gene
HIPAA	Health Insurance Portability and Accountability Act
HPMC	Hydroxypropyl methylcellulose
H&Y	Hoehn and Yahr
ICH	International Conference on Harmonization
IRB	Institutional Review Board
IRE	Iron-responsible element
IRP1	Iron Regulatory Protein 1
LBD	Lewy Bodies Dementia
LP	Lumbar Puncture
MAD	Multiple Ascending Dose
MCI	Mild Cognitive Impairment
MDS-UPDRS	MDS-United Parkinson's Disease Rating Scale
MMSE	Mini-Mental State Examination
MRI	Magnetic Resonance Imaging
mRNA	Messenger Ribonucleic Acid
NIH	National Institutes of Health
NOAEL	No observed adverse effect level
NPH	Normal Pressure Hydrocephalus
OHRP	Office for Human Research Protections
p-tau	Phosphorylated tau
PD	Parkinson's disease
PHI	Protected Health Information
PI	Principal Investigator
PK	Pharmacokinetic
PSP	Progressive Supranuclear Palsy
QD	Once a Day
QID	4 Times a Day
QT	Interval seen in electrocardiogram (ECG) test
QTc	Interval seen in QT (ECG) test
sAPP	Soluble Amyloid Precursor Protein
sAPP α	Soluble Amyloid Precursor Protein alpha
sAPP β	Soluble Amyloid Precursor Protein beta
SAD	Single Ascending Dose

SAE	Serious Adverse Event
SH-SY-5Y	Human Derived Cell Line
SILK™	Stable Isotope Labeling and Kinetics
SD	Standard Deviation
$t_{1/2}$	Half-life
tau	Tau protein
TID	Three Times a Day
TPN	Total Parenteral Nutrition
WAIS-IV	Weschler Adult Intelligence Scales, 4th edition

Table of Contents

1	PROTOCOL SYNOPSIS	11

1 PROTOCOL SYNOPSIS

PROTOCOL TITLE	A Multicenter, Randomized, Double-Blind, Placebo-Controlled, Dose-Finding Study to Evaluate the Safety, Tolerability, Pharmacokinetic and Pharmacodynamic Effects of Posiphen® in Subjects with Early Alzheimer's Disease (AD) or Early Parkinson's Disease (PD)
STUDY DESIGN	
This study will be conducted in two parts.
 
Part 1 will evaluate the safety, tolerability, and pharmacokinetics of Posiphen in 14 Early AD and 14 Early PD patients at the following dose:
 
 • 80 mg QD 
Each group will include 14 Early AD patients, randomly assigned, 10 to Posiphen and 4 to placebo and 14 Early PD patients randomly assigned, 10 to Posiphen and 4 to placebo.
 
Part 1 of the study will also include exploratory measures of pharmacodynamics and efficacy of Posiphen with target engagement, pathway engagement and functional/cognitive measures, including the degree of memory loss and cognitive function in AD patients as well as the degree of motor impairment and non-motor symptoms and quality of life in PD patients.
 
Subjects who drop out during the initial 3-week at-home treatment period will be discontinued and replaced by new subjects. If 4 subjects are discontinued due to adverse events, no additional subjects will be recruited until a safety review has been conducted.
 
After Part 1 has been completed study data will be locked to allow a full analysis of biomarker data to sensitize analysis plans in Part 2.
 
Part 2 will evaluate the safety, tolerability, and pharmacokinetics of Posiphen in 40 patients with early PD, randomly assigned to the following dose levels, 10 patients per dose level:
 
 • 5 mg QD • 10 mg QD • 20 mg QD • 40 mg QD 
Part 2 of the study will also include exploratory measures of pharmacodynamics and efficacy of Posiphen in Early PD patients with target engagement, pathway engagement and functional/cognitive measures, including the degree of motor impairment as well as other non-motor symptoms and quality of life in PD patients.

	Subjects who drop out during the initial 3-week at-home treatment period will be discontinued and replaced by new subjects. If 4 subjects are discontinued due to adverse events, no additional subjects will be recruited until a safety review has been conducted.
DURATION OF STUDY PARTICIPATION	Each subject will have up to a 42-day screening period, a baseline visit including a lumbar puncture (LP), followed by 25±2 days of treatment at home, followed by an in clinic visit that includes treatment and a 6-hour LP procedure.
SUMMARY OF INVESTIGATIONAL PRODUCT	
Part 1: Posiphen/placebo 80 mg QD, taken orally for 25±2 days by Early AD and PD patients.
 
Part 2: Posiphen at 5, 10, 20, or 40 mg QD, taken orally for 25±2 days by Early PD patients.

SUMMARY OF KEY ELIGIBILITY CRITERIA: FOR AD	
 • Diagnosis of early AD • Age 45 or older • MMSE 18-28 • Clinical Dementia Rating (CDR) of 0.5 or 1.0
SUMMARY OF KEY ELIGIBILITY CRITERIA: FOR PD	
 • Diagnosis of early PD • Age 45 or older • MMSE 18-30 • Hoehn & Yahr ≤ 4
PRIMARY OUTCOME MEASURES	
Aim 1. Safety and Tolerability
 
Aim 2. PK of Posiphen in Plasma

EXPLORATORY MEASURES	
TARGET ENGAGEMENT
 
Levels of neurotoxic proteins in blood, plasma and CSF:
 
 • aSYN and Aβ monomers and dimers, and infective oligomers • Aβ38, Aβ40, Aβ42 • soluble Amyloid Precursor Proteins: sAPPα and sAPPβ • T-Tau and P-Tau proteins 
PATHWAY ENGAGEMENT
 
Levels of proteins involved in the toxic cascade leading to nerve cell death in blood, plasma and CSF

	
• Neurotransmitters• Neurotrophic factors• Inflammatory factors• Synaptic factors• Control proteins that should not change 
FUNCTIONAL/COGNITIVE MEASURES
 
PD: MMSE, WAIS-IV, MDS-UPDRS
 
AD: MMSE, WAIS-IV, ADAS-Cog 14, CDR

--	--

2 INTRODUCTION

Currently, there is no treatment available to stop or reverse the progression of Alzheimer's (AD) and Parkinson's disease (PD). Neurodegenerative diseases such as AD and PD share many common characteristics, including the central role of neurotoxic aggregating proteins in their pathogenesis. Amyloid β (A β) and tau aggregates (senile plaques and neurofibrillary tangles, respectively) have been traditionally associated with AD, while α -synuclein (α SYN) aggregates (Lewy bodies) have been associated with PD. However, it is becoming increasingly clear that all these proteins are involved in both diseases and that aggregation of one can lead to accumulation of another. Furthermore, in several studies of brains from older patients, a high percentage of all AD brains present mixed pathologies, such as Lewy body disease. Several clinical trials targeting just one (often A β) of the neurotoxic aggregating proteins have failed. Finally, other fragments of Amyloid β Precursor Protein (APP) have been implicated in AD pathology. Collectively, these facts point to the need for development of combination therapies that target multiple neurotoxic aggregating proteins simultaneously, if we are to have a good chance of at least halting disease progression.

Posiphen has a unique mechanism of action, in that it inhibits the translation and, therefore, reduces the levels of several neurotoxic aggregating proteins both *in vitro* and *in vivo*, including α -Synuclein (α SYN), Amyloid Precursor Protein (APP), its fragments, and tau. All three proteins have been implicated in the pathogenesis of PD. Furthermore, at older ages, there is a high incidence of patients with mixed pathologies, such as PD dementia. Therefore, it is reasonable to hypothesize that inhibiting expression of all three proteins should lead to a better efficacy outcome in PD patients than inhibiting just one.

Posiphen's safety has been established in three Phase I clinical studies by [name] et al. Importantly, Posiphen normalized levels of α SYN, APP, and tau in the cerebrospinal fluid (CSF) of mildly cognitively impaired (MCI) patients at a dose of 4x60 mg/day (Protocol QR12001). Preclinical data proves Posiphen's efficacy in restoring colonic motility in a human *SNCA*^{453T} tg mouse model of early PD, in restoring memory and learning in an *APP/PS1* transgenic (tg) mouse model of AD, restoring axonal transport in DS trisomic mice, preserving memory and learning in traumatic brain injury rats and preserving the retina in acute glaucoma.

α SYN, APP, and tau contribute to the progression of AD and PD in similar ways: they impair axonal transport and lower neurotransmitter and neurotrophic factor release, they cause inflammation, they form aggregates, and, finally, they lead to nerve cell death. In our *in vitro* and *in vivo* preclinical studies, Posiphen has normalized all those actions.

We have conducted a proof-of-concept study in mildly cognitive impaired patients at 4x60 mg/day (Protocol QR12001) and found that Posiphen lowers levels of neurotoxic proteins and of inflammatory markers. Presently, we are testing Posiphen in the DISCOVER study at 1x60, 2x60 and 3x60 mg/day for up to 25 days to see if it changes the synthesis and degradation

kinetics of A β in a stable isotope labelling kinetic (SILK) study. The DISCOVER study is ongoing through the ADCS and is planned for 24 patients to be enrolled; currently, approximately half of the study has been enrolled, and there have been no severe AEs or SAEs attributed to Posiphen reported.

From our animal data, we found that Posiphen works in more than Alzheimer animals, because it inhibits more than one neurotoxic protein. We found that in transgenic AD and PD animals it lowers levels of neurotoxic proteins and restores the affected function. Therefore, we want to test Posiphen in a comparison study of AD and PD patients and measure not just target engagement, but also pathway engagement.

From our animal data, we also found that the doses used to show an effect on neurotoxic proteins are very high and that we can see an effect of Posiphen at much lower doses. Therefore, we are testing Posiphen in a randomized dose de-escalation study to see what the lowest effective dose is in humans.

In this study, we want to find out if the animal Posiphen data can be replicated in humans and show target and pathway engagement in CSF. Target engagement means that Posiphen would lower and normalize the levels of neurotoxic proteins in CSF. Pathway engagement means that Posiphen would increase levels of neurotransmitters, neurotrophic factors, and lower levels of inflammatory and neurodegeneration markers in both AD and PD patients. By examining all these factors in early AD and PD patients, we will specify the biomarkers that change with Posiphen treatment, which will be used in later phase studies. Additionally, we will assess function and cognition, so we can make sure that Posiphen has no deleterious effect and potentially identify any improvement. Collectively, these endpoints will help assess the efficacy of Posiphen and drive it to late phase clinical studies.

2.1 Objectives

Study objectives include assessing safety, tolerability, and pharmacokinetics of Posiphen as well as exploring pharmacodynamics and efficacy in Early AD and Early PD patients with target engagement, pathway engagement and functional/cognitive measures being the focus of the exploratory analyses. This study will be conducted in two parts as follows.

Part 1

Primary objectives are to assess the safety, tolerability, and pharmacokinetics of Posiphen in 14 Early AD and 14 Early PD patients at a dose of 80 mg QD for 25 \pm 2 days.

Each group will include 14 Early AD patients, randomly assigned, 10 to Posiphen and 4 to placebo and 14 Early PD patients randomly assigned, 10 to Posiphen and 4 to placebo.

Exploratory objectives will include investigating the pharmacodynamics and efficacy of Posiphen as well as the relationship between them. Efficacy assessments will focus on the following:

- degree of memory loss and cognitive function in AD patients
- degree of motor impairment and non-motor symptoms and quality of life in PD patients.

Part 2

Primary objectives are to assess the safety tolerability, and pharmacokinetics of Posiphen in 40 patients with early PD, 10 patients randomly assigned to each of the following dose levels, given for 25 ± 2 days:

- 5 mg QD
- 10 mg QD
- 20 mg QD
- 40 mg QD

Exploratory objectives will include investigating the pharmacodynamics and efficacy of Posiphen as well as the relationship between them. Efficacy assessments will focus on the degree of motor impairment in PD as well as other non-motor symptoms and quality of life.

2.2 Endpoints

SAFETY AND TOLERABILITY

- adverse events
- physical examinations
- vital signs
- 12-lead ECGs
- clinical laboratory values

PHARMACOKINETICS

PK parameters will minimally be determined, as data permit: Area under the curve (AUC), Cmax, Tmax, $t_{1/2}$, and CL.

Additionally, the following Exploratory Objectives will be evaluated:

TARGET ENGAGEMENT

Levels of neurotoxic proteins in blood, plasma and CSF

- aSYN and A β monomers and dimers, and infective oligomers
- A β 38,40,42
- soluble Amyloid Precursor Proteins: sAPP α and sAPP β
- T-tau and P-tau protein

PATHWAY ENGAGEMENT

Levels of proteins involved in the toxic cascade leading to nerve cell death in blood, plasma and CSF

- neurotransmitters
- neurotrophic factors
- Inflammatory factors
- Synaptic factors
- Control proteins that should not change

FUNCTIONAL/COGNITIVE MEASURES

PD: MMSE, WAIS-IV, MDS-UPDRS

AD: MMSE, WAIS-IV, ADAS-Cog 14, CDR

3 PRELIMINARY STUDIES

The following is a brief summary of the available information on Posiphen. Detailed information can be found in the current Posiphen Clinical Investigational Brochure.

3.1 Summary of Non-Clinical Findings

In wild type mice, Posiphen lowered brain APP and A β levels by up to 60% ([Lahiri 2007](#), [Cullen 2006](#)). In APP transgenic AD mice, Posiphen led to a decrease in APP levels, improved neuronal stem cell survival and increased levels of brain-derived neurotrophic factor (BDNF) ([Marutle 2007](#); [Kadir 2008](#), [Lilja 2013](#)). Chronic administration of Posiphen to APP transgenic mice totally prevented decline in memory and learning as well as in long-term potentiation at brain and plasma concentrations that are 10 times lower than originally published. These plasma levels are attainable with low oral dosing in humans ([Teich 2018](#)). In alpha-synuclein (α SYN) transgenic PD mice, Posiphen restored gut motility to normal and lowered α SYN in the brain and gut of the tg PD mice. Again, the efficacious levels were 10 times lower than originally published ([Kuo 2019](#)). In DS trisomic mice Posiphen fully restored axonal transport *in vitro* and *in vivo* (Mobley Lab, UCSD, 2019; manuscript submitted for publication). In summary, Posiphen is a translational inhibitor of APP and α SYN and fully restores function at doses that are very low and very safe.

Posiphen was not mutagenic or clastogenic as assessed by *in vitro* assays.

The cardiac electrophysiological properties of Posiphen tartrate were negative *in vitro* using human ether-a-go-go related gene (hERG) transfected human embryonic kidney cells (HEK 293). Posiphen did not adversely affect the interval seen in an electrocardiogram (ECG) test (QT (or QTc)) interval.

Toxicity studies in dogs showed brain toxicity (ataxia and tremors/twitching) and gastrointestinal (GI) toxicity at 30 mg/kg/day, which was dose-dependent and reversible. The no observed adverse effect level (NOAEL) was 20 mg/kg/day in dogs. Posiphen readily crosses the blood-brain barrier. The signs/symptoms noted at high doses of Posiphen may be related to cholinergic manifestations. In *in vitro* assays, Posiphen showed minimal inhibition of AChE or BChE (Butyrylcholinesterase) activity, however, a metabolic product of Posiphen, N1-norposiphen demonstrated acetyl cholinesterase inhibitory activity ([Yu 2013](#)). There were no effects on the reproductive organs associated with 4-week exposure to Posiphen in male or female rats or dogs.

3.2 Summary of Clinical Findings

Three Phase 1 studies have been conducted with Posiphen ([IB 2019](#)). The first was a single ascending dose (SAD) study in healthy volunteers; the second was a multiple ascending dose (MAD) study in healthy volunteers, and the third one was a pharmacokinetic

(PK)/pharmacodynamic study of CSF obtained from mild cognitively impaired participants (Protocol QR12001).

In the MAD trial, Posiphen was administered orally in doses of 20, 40, and 60 mg 4 times a day (QID). The first two treatments were administered for 7 days, and the third, for 10 days. Single doses were given on the first and last day to determine the pharmacokinetics of the drug. In general, the drug was well tolerated, resulting in no serious or severe adverse events and only one premature discontinuation, a subject in the 60 mg group discharged because of nausea, vomiting, dizziness and “feeling warm.” The incidence of adverse events, all either mild or moderate severity, also occurred with similar frequency in the placebo group. The most common AEs were dizziness, headache, and nausea/vomiting.

Posiphen was absorbed rapidly after oral administration, achieving maximum plasma and CSF concentration (C_{max}) within 1.2 - 1.5 hours. For the 40 and 60 mg doses, with fully defined plasma profiles, the mean terminal $t_{1/2}$ ’s were 3.80 ± 0.88 and 5.23 ± 1.24 hours, respectively after a single dose and 3.53 ± 1.03 and 4.104 ± 0.91 hours, respectively, after repeat dosing. The half-life ($t_{1/2}$) of the plasma concentrations at the lower doses could not be calculated accurately. The C_{max} increased disproportionately with dose (24, 144, and 2310 ng.h/mL after a single dose of 20, 40, and 60 mg, respectively and 110, 134, and 2101 ng.h/mL after multiple doses of 20, 40, and 60 mg, respectively).

In the proof of mechanism of action study (Protocol QR12001), the PK of Posiphen was measured after 10 days of administration (4x60 mg) over 6 hours in CSF and plasma of the AD participants. The pharmacodynamics of a number of biomarkers was compared for 6 hours before the first dose at day 0 and after the last dose at day 11 of Posiphen administration. We found that the plasma concentrations of Posiphen overlapped with the plasma concentrations found in the MAD study. In this study, the N1 metabolite reached about 10 to 15%, while the level of the N8 metabolite reached about 20 to 25% of the Posiphen levels measured in plasma.

Because a substantial proportion of the adverse events observed in AD patients treated with cholinesterase inhibitors appear to reflect the cholinomimetic properties of molecules in this class, Posiphen’s highest tolerated dose is determined by the levels of the N1-norposiphen in blood and brain.

While the $t_{1/2}$ of Posiphen in plasma was 5 hours as seen in the SAD and MAD studies, the $t_{1/2}$ in CSF/brain was longer than 12 hours. Concentrations of Posiphen in the brain, extrapolated from blood and CSF, were 8 times higher than in plasma. 10 days of treatment with Posiphen normalized CSF levels of sAPP, tau, α SYN and a series of inflammatory markers. The concentration and persistence of Posiphen in the brain suggest that much lower doses of drug administered once daily could achieve the desired pharmacological effect.

4 BACKGROUND AND STUDY OVERVIEW

4.1 Background

A major pathological hallmark of AD is the appearance of plaques and tangles in the brain and of PD the appearance in the gut and in the brain of aSYN aggregates that form Lewy bodies. In both diseases these aggregates are thought to occur one or two decades prior to overt symptom development. Recent research has shown that soluble forms of phosphorylated tau (p-tau) and A β may also contribute to neuronal loss and that PD as well as AD carry a high load of inflammation and microglia activating factors that contribute to neurodegeneration.

For small molecules that target biomarker levels, studies using CSF and plasma sampling in humans can provide data to demonstrate that a drug crosses the blood-brain barrier and engages the relevant target, and to describe the relationship between blood levels and CNS effects.

Repeated sampling through a lumbar CSF catheter for 6 hours can mirror image, what happens in the brain as to the levels of aSYN monomers and dimers, A β monomers and dimers as well as other biomarkers and help guide the development of drugs targeting neurotoxic aggregating proteins.

Posiphen is the (+) enantiomer of phenserine, an AChE inhibitor which had been tested in several AD studies without significant evidence of efficacy. While phenserine inhibits AChE, Posiphen has no AChE activity itself and develops some activity in vivo with the metabolism to N1-bisnorposiphen. In vivo phenserine has about 200 times more AChEI activity than Posiphen's metabolite N1-bisnorposiphen. Posiphen absorption is affected by food; however, at steady state there is no effect on the PK analyses results.

Posiphen has been found to significantly reduce soluble APP and A β as well as tau, p-tau and aSYN in the rodent brain and in human CSF. In preliminary studies in animals and humans, inhibition of APP, A β , tau, p-tau and aSYN occurs at levels 6 to 10 times lower than the levels causing cholinomimetic effects.

Posiphen acts at the 5'UTR of the aSYN and APP mRNA and lowers their protein expression levels in animal models; it also decreased aSYN and sAPP levels in human CSF. Our data suggests that these effects are achieved via the same mechanism: the 5'UTRs of these mRNAs form a complex with iron regulatory protein 1 and Posiphen stabilizes the complex, thereby inhibiting the translation of these mRNAs.

As Posiphen inhibits the synthesis of aSYN and APP, as well as other neurotoxic aggregating proteins, it might have a broader spectrum of activity than PD and AD. By protecting neurons from dying it has a disease-modifying effect in PD, AD as well as other neurodegenerative disorders.

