7.2 Dosage

The study drug is to be taken orally; one capsule, once a day in the morning, with or without food, for 25 days \pm 2 days at home (depending on when the confinement visit is scheduled).

Participants must take 80% of all doses (across 25 \pm 2 days). Bottles will be examined in clinic at the pre-confinement visit to assess compliance overall and in the last week.

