9.4.2 Confinement Visit

The confinement visit will consist of the following: admission procedures, Time 0 blood and CSF sampling, administration of last dose of study drug, 6-hours of blood and CSF sampling, at least a 1-hour observation period while subject remains on bed rest with the observation period

to be extended as clinically necessary as per the Investigator's decision, and discharge procedures. Subjects will be provided with sleeping accommodations during this visit, if necessary, and maybe permitted to remain overnight per investigator discretion in the event there are adverse events associated with the study medications or study procedures.

Subject confinement visit can be split over two (2) consecutive days should the investigator feel that the neuropsychological tests are better completed one day before the lumbar puncture.

Period 1: Admission

Subjects should arrive fasted in the early morning after an overnight fast. Clinical safety labs will be drawn and sent to the central lab for analysis.

Study drug compliance over the preceding days will be assessed. If there is an insufficient level of drug compliance (less than 80% overall), the site must consult with the Project Directors and Medical Monitor) regarding timing and conduct of the remaining confinement visit procedures. It is possible that subjects will be discontinued early from the study due to insufficient study drug compliance.

Admission visit procedures include conducting a Physical and Neurological Exam, administering functional and cognitive evaluations and C-SSRS, collecting vital signs, ECG, clinical labs, reviewing and recording adverse events and concurrent medications.

Period 2: 6-Hour Sampling

If no medical or compliance concerns are identified during the admission procedures, the subject will move on to the 6-Hour Sampling Phase, which entails the following procedures:

1. Place an intravenous line for blood sampling. Alternatively, blood may be sampled by direct venipuncture if deemed appropriate by the PI.
2. Place the CSF catheter.
3. Collect initial samples of blood and CSF (Hour 0).
4. Administer last dose of assigned study drug after the 0 hour sampling.
 - a. Collect CSF (6 mL) and blood (10mL) every hour at the following time points: 1, 2, 3, 4, 5, 6 hours.
 - i. CSF and blood should be taken within \pm 10 mins of hourly times.

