12.2.4 Blood Samples for Exosomes

Blood will be collected in the morning, after an overnight fast, in EDTA tubes and will be subjected to two sequential centrifugations to generate platelet-poor plasma within one hour from the blood draw, as described in the Laboratory Manual. **Note** - for exosomes draws at the confinement visit after the 0-hour sample, strict fasting is no longer required. Low lipid foods (e.g., apple, banana, bread) are allowed.

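### Steady state does not by itself protect the once-daily Day 25 plasma profile from food, and the timing of food around that dose is only partly fixed and not recorded

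*Protocol*

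**What the plan says.** **On food.** Protocol 4.1 says: "Posiphen absorption is affected by food; however, at steady state there is no effect on the PK analyses results". It gives no figure, study or regimen in support.

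**On half-life.** Protocol 3.2 reports mean terminal plasma half-lives for 40 and 60 mg: these "were 3.80 ± 0.88 and 5.23 ± 1.24 hours, respectively after a single dose", and "3.53 ± 1.03 and 4.104 ± 0.91 hours, respectively, after repeat dosing". The same section gives a summary value: the half-life "of Posiphen in plasma was 5 hours as seen in the SAD and MAD studies". The maximum concentration is reached within 1.2 to 1.5 h. The multiple-dose study described there, and the study in cognitively impaired patients, dosed four times a day.

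**On feeding at home.** Protocol 7.2 prescribes "one capsule, once a day in the morning, with or without food". The sentence goes on to tie this to the at-home period.

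**On feeding at the Day 25 profile:**
- Protocol 9.4.2: "Subjects should arrive fasted in the early morning after an overnight fast". Footnote i of Appendix 1 also requires the 0 h safety bloods to be fasted.
- Protocol 9.4.2 and 12.2.1: the last dose follows the 0 h sample, and 12.2.1 adds only that it must precede the 1 h sample.
- Protocol 12.2.4, on exosome draws after the 0 h sample: "strict fasting is no longer required. Low lipid foods (e.g., apple, banana, bread) are allowed".

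**On use of the profile.** Plasma PK is a primary outcome (synopsis, Aim 2). SAP 5.4 derives the parameters from the Day 25 samples at 0 to 6 h, and SAP 6.4.2 uses Cmax and AUC for the 5 to 80 mg dose comparison and dose-proportionality analysis. Neither Schedule of Events, nor SAP 5.4, 6.4 or 7.4, mentions food.

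**The concern.** If food alters absorption, a plasma profile taken after one oral dose reflects the feeding state at that dose. Accumulation can dampen this only if earlier doses contribute a material share of the profile. Four-times-daily dosing could provide such a share. Once-daily dosing of a drug with a plasma half-life of about 4 to 5 h would not be expected to.

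At stake is avoidable between-patient variation in a primary outcome that rests on one 6-hour profile per patient, with 10 patients per dose in the PD cohorts. If food and dose times are not recorded, the variation cannot be explained afterwards. Protocol 4.2 also attributes likely cholinergic adverse events mainly to Cmax, so unexplained spread in Cmax would make exposure-safety readings harder too.

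**Working it through.** The documents state no carry-over or food-effect figure, so there is no figure of the plan's own to reproduce.

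**Step 1: carry-over from the previous dose.** Residual r = 2^(−τ/t½); accumulation = 1/(1 − r). Half-lives are from Protocol 3.2, and τ = 24 h from 7.2. For comparison, τ = 6 h represents four-times-daily dosing if evenly spaced.

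| t½ (h) | r, 24 h | accumulation, 24 h | r, 6 h | accumulation, 6 h |
|---|---|---|---|---|
| 3.53 | 0.9% | 1.01 | 30.8% | 1.44 |
| 4.104 | 1.7% | 1.02 | 36.3% | 1.57 |
| 5 | 3.6% | 1.04 | 43.5% | 1.77 |
| 5.23 | 4.2% | 1.04 | 45.1% | 1.82 |
| 6.47 (5.23 + 1 SD) | 7.6% | 1.08 | 52.6% | 2.11 |

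Example: 24/5.23 = 4.59 half-lives, 2^(−4.59) = 0.042, and 1/(1 − 0.042) = 1.04. For the residual to reach 10% the half-life would have to be 24 × ln 2/ln 10 = 7.22 h.

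**Step 2: share of the Day 25 AUC0-6h from earlier doses.** This uses superposition in a one-compartment model with first-order absorption, the absorption rate solved from Tmax 1.2 to 1.5 h, and linear kinetics. For half-lives of 3.53 to 5.23 h the share s is 1.0% to 4.7% once daily and 33.8% to 48.5% at 6-hourly dosing.

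**Step 3: how much of a food effect on the last dose gets through.** If food multiplies the bioavailability of that dose by f, the AUC0-6h ratio is s + f(1 − s). The values of f are assumptions, because the documents give neither the size nor the direction of the effect.
- f = 0.7, once daily: 0.010 + 0.7 × 0.990 = 0.703, up to 0.047 + 0.7 × 0.953 = 0.714. That is a fall of 29.7% to 28.6%. Modelled Cmax falls by almost the same amount (ratio 0.703 to 0.713).
- f = 0.5, once daily: 0.505 to 0.524, a fall of 49.5% to 47.6%.
- f = 0.7, 6-hourly: 0.338 + 0.7 × 0.662 = 0.801, up to 0.485 + 0.7 × 0.515 = 0.846. That is a fall of about 20% to 15%.

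Whatever f is, once-daily dosing passes on nearly all of it.

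**Step 4: what a compliant patient may do.** Up to the 0 h sample all patients are fasted. After it, two freedoms overlap: the capsule may be given at any point before the 1 h sample, and low-lipid food may be eaten. No order or interval between them is set. Eating before the capsule, with it, soon after it, or not at all during sampling are all within the rules. With a Tmax of 1.2 to 1.5 h, the first three place food within the absorption window.

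**The case against.** The strongest reply is that feeding is largely controlled. All patients in both Parts arrive after an overnight fast and stay fasted to the 0 h draw, the dose comes after that draw, and later food is limited to low-lipid items. Home meals under 7.2 hardly matter, because by the arithmetic above earlier doses contribute little to the profile. This stands. A reader might infer that the fed or fasted state at the Day 25 dose is uncontrolled, or that 7.2 governs that dose. The documents support neither. The gap is the unset order and interval between capsule and food after the 0 h sample, and low-lipid food may have a smaller effect than a full meal.

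Second, the 4.1 sentence may report an observed result rather than argue from accumulation. Protocol 3 refers to the investigator's brochure for detail, and the introduction describes an ongoing isotope-labelling study with a 60 mg once-daily arm. So the sentence is unsupported in these documents but not shown to be false, and one cannot say it rests on four-times-daily data.

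Third, linear kinetics are an approximation. Protocol 3.2 reports Cmax rising out of proportion to dose, and its repeat-to-single Cmax ratios (110/24 = 4.6, 134/144 = 0.93, 2101/2310 = 0.91) do not match the modelled 6-hourly accumulation of 1.44 to 1.82. Half-life could not be calculated accurately at lower doses, so carry-over at 5 to 20 mg is less certain.

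Fourth, the case report form and Laboratory Manual are not available here and may already capture intake.

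**Conclusion.** The point holds in a limited form. On the protocol's own mean plasma half-lives, 0.9% to 4.2% of the previous dose remains at 24 h (7.6% at one SD above the longest mean). Steady state therefore does not by itself protect the Day 25 plasma profile from a food effect. After a fasted 0 h sample, food within the absorption window can differ between compliant patients, and neither the protocol text, the Schedule of Events nor the SAP records or uses it.

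The conclusion assumes linear kinetics and half-lives measured at 40 and 60 mg. It concerns plasma only: at the stated CNS half-life of over 12 h, at least 2^(−24/12) = 25% carries over.

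A reader might go further and put a figure on the added variance by assuming half the patients fed and half fasted. A reader might also infer a biased dose-proportionality slope because the 80 mg group comes only from Part 1. The documents support neither step. No such mix is described, the size of the food effect is not given, and Protocol 4.2 and 6.7 and SAP 3.2 state that conduct is identical in the two Parts. This is a cheap improvement to a primary outcome, not a flaw that undermines the PK analysis.

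**What to change.** 1. In Protocol 4.1, limit the food sentence to the regimen and data it rests on, and cite them.
2. Reconcile Protocol 9.4.2, 12.2.1 and 12.2.4 so that the timing of the Day 25 dose relative to food is the same for all patients in both Parts. The choice of condition is the sponsor's.
3. Record the clock time of that dose and the time and content of the first food around it, if these are not already captured.
4. In SAP 6.4.2, list this information with the PK parameters and repeat the Cmax and AUC models with feeding state as a factor, as a sensitivity analysis. With 10 patients per dose the food estimate will be imprecise, so it serves as a check and not as a test of a food effect.

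The cost is a few sentences of protocol and manual wording, a little more data capture and one extra model, with slightly less flexibility for patients and sites on the sampling day.
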